### **3.c Definitions of Adverse Events**

Adverse events will include medication side effects including gastrointestinal upset symptoms such as nausea, vomiting, flatulence, diarrhea, dyspepsia, and abdominal pain. Other medication side effects may include rash or itching.

### **3.d Classification of Events**

#### **i Severity**

All expected adverse events are of mild severity.

For this study, the following standard adverse event (AE) definitions are used:

Adverse event: Any unfavorable and unintended sign, symptom, or disease temporally associated with the use of a medical treatment or procedure, regardless of whether it is considered related to the medical treatment or procedure.

Serious Adverse Event (SAE): Any AE related to the study drug that results in any of the following circumstances: death, life-threatening, event requiring inpatient hospitalization or prolongation of existing hospitalization, persistent or significant disability/incapacity

AEs are graded according to the following scale:

Mild: An experience that is transient and requires no special treatment or intervention. The experience does not generally interfere with usual daily activities.

Moderate: An experience that is alleviated with simple therapeutic treatments. The experience impacts usual daily activities.

Severe: An experience that requires therapeutic intervention. The experience interrupts usual daily activities. If hospitalization (or prolongation of hospitalization) is required for treatment of something related to the study drug, it becomes a SAE.

The study uses the following AE attribution scale:

Not related: The AE is clearly not related to the study procedure (i.e., another cause of the event is most plausible and/or a clinically plausible temporal sequence is inconsistent with the onset of the event).

Possibly related: An event that follows a reasonable temporal sequence from the initiation of study procedures, but that could readily have been produced by a number of other factors.

Related: The AE is clearly related to the study procedures.

---

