### **3.c Method for Assigning Subjects to Treatment Groups**

If a participant is using VET and therefore eligible for the RCT portion of the study, they will be randomized according to the preset randomization allocation to determine if she is in the treatment arm of the randomized control trial (D-mannose plus vaginal estrogen therapy) or the control arm of the randomized controlled trial (vaginal estrogen therapy only).

If a patient is not using VET but meets all other study requirement then she would be eligible only for the Observational arm of the study.

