### **3.f Packaging**

D-mannose is the only study drug and will be in its original container from the manufacturer. The study team has selected NOW D-mannose pure powder as the D-mannose to be used in the

RCT. The patient label for the treatment arm of the randomized, controlled portion of the study will be updated to maintain blinding of the patient to which nutraceutical is being studied.

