### 3.g Blinding of Study Drug

For the treatment arm of the RCT, the D-mannose powder will be ordered and distributed by the research team. The manufacturer label will be covered up/removed and a study label stating contents of a nutraceutical will be used to maintain patient blinding to which nutraceutical is being used. The research team will not be blinded to the study drug. There are no placebos being used in this study.

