#### **ii Institutional Data and Safety Monitoring Board**

After the first ten participants have completed the study, review of adverse events experienced by the first ten participants will be compiled and assessed. The data and compiled information will be made available to an institutional data and safety monitoring board (DSMB) for

---

independent analysis. A similar sequence of events will occur after half of the participants in the study have completed the study and again at completion of all participants in the study.

The DSMB will include an individual with expertise and experience with conducting randomized controlled trials in the field of obstetrics and gynecology, an individual with expertise in urology and experience with recurrent UTI, and a biostatistician.

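### Serious adverse events are limited to those related to D-mannose, so no control event can qualify, and side effects are estimated in the D-mannose plus VET arm only

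*Combined protocol and SAP*

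**What the plan says.** Section F3 3.d (Severity) defines an adverse event broadly, "regardless of whether it is considered related to the medical treatment or procedure". The SAE definition that follows is narrower: "Any AE related to the study drug that results in any of the following circumstances: death, life-threatening", or one of the other listed serious outcomes. The Severe grade repeats the restriction: "If hospitalization (or prolongation of hospitalization) is required for treatment of something related to the study drug, it becomes a SAE". The attribution scale in the same section has three levels and is worded for study procedures, not study drug. Its top level reads "The AE is clearly related to the study procedures".

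E3 3.f states that "D-mannose is the only study drug and will be in its original container from the manufacturer". Under E3 3.c the control arm receives VET alone, and E3 3.g adds: "There are no placebos being used in this study".

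G3 calculates the incidence of side effects and of discontinuation with the D-mannose plus VET arm as both numerator and denominator. It plans no control-arm rate and no between-arm safety comparison. The matching aim in C2 is descriptive.

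**The concern.** Seriousness and causality are separate attributes of an event, and the SAE definition merges them. Because relatedness to D-mannose is a condition of being an SAE, the label is in effect closed to women who are not given D-mannose. It also depends on a causality judgement for women who are. Any later count labelled SAE could not be compared between arms.

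The G3 estimate has a related weakness. The expected effects listed in F3 3.c and 3.d are mostly non-specific gastrointestinal symptoms, which controls can have too. A one-arm proportion cannot separate drug effects from background symptoms. The central hypothesis in A2 describes D-mannose as tolerable as well as effective, and the trial has a randomised comparator that could inform that claim.

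**Working it through.** **SAE definition: the sections side by side**

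1. An event is an SAE only if it (a) has a listed serious outcome and (b) is related to the study drug (F3 3.d, stated twice).
2. The study drug is D-mannose and nothing else (D1, E3 3.f). VET is background treatment.
3. Controls take VET alone (E3 3.c), with no placebo (E3 3.g). The study dispenses D-mannose only to the RCT treatment arm (E3 3.h).
4. Condition (b) therefore fails for every control event, barring off-protocol use of an over-the-counter product. It also fails for any serious event judged unrelated in an arm that takes D-mannose.
5. The attribution scale does not settle condition (b). It refers to study procedures, and nothing says whether the middle level, possibly related, counts as related.
6. No other section gives a broader SAE definition.

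**Side-effect estimate: size**

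The plan states no side-effect rate for this trial, so there is no figure to reproduce. A D-mannose rate can be derived from the cited 2 g trial (B1, D2): 27.2% side effects on nitrofurantoin, and a relative risk of 0.276 (95% CI 0.132 to 0.574) for D-mannose against nitrofurantoin. The 27.2% is treated as fixed.

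- Point: 0.272 × 0.276 = 7.5%; × 60 = 4.5 women.
- Lower: 0.272 × 0.132 = 3.6%; × 60 = 2.2 women.
- Upper: 0.272 × 0.574 = 15.6%; × 60 = 9.4 women.

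These give working counts of 5, 2 and 9 out of 60 (60 per arm from G1, before dropout). At 5/60, G3 reports 8.3%, Clopper-Pearson 95% CI 2.8 to 18.4%, whatever the controls show.

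The between-arm difference uses Newcombe's interval. With d = p1 − p2 and Wilson limits (l, u) for each arm:

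- lower = d − √[(p1 − l1)² + (u2 − p2)²]
- upper = d + √[(u1 − p1)² + (p2 − l2)²]

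For 5/60 against 0/60, in percentage points, the Wilson limits are 3.6 to 18.1 and 0 to 6.0:

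- lower = 8.3 − √(4.7² + 6.0²) = 0.7
- upper = 8.3 + √(9.7² + 0²) = 18.1

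(Computed from unrounded values.) All control counts below are assumptions.

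| D-mannose | Control | Difference, points (95% CI) |
|---|---|---|
| 5/60 | 0/60 | 8.3 (0.7 to 18.1) |
| 5/60 | 2/60 | 5.0 (-4.3 to 15.0) |
| 5/60 | 5/60 | 0 (-10.8 to 10.8) |
| 2/60 | 0/60 | 3.3 (-3.2 to 11.4) |
| 2/60 | 2/60 | 0 (-8.4 to 8.4) |
| 9/60 | 0/60 | 15.0 (5.8 to 26.1) |
| 9/60 | 9/60 | 0 (-13.1 to 13.1) |

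Within each D-mannose count the G3 output is the same, although the excess over control differs.

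**The case against.** The strongest reply concerns weight. AEs are defined regardless of relatedness, graded, and noted in each subject's file (F3 3.e). Charts are reviewed at three months (F3 3.a). For the DSMB, "review of adverse events experienced by the first ten participants will be compiled and assessed", with no restriction by arm and with later reviews at the halfway point and at completion. The plan has no SAE table and no SAE-based rule, so no planned analysis goes wrong. All of this stands: the fault is in classification, not capture. It does not make the definition sound, because the DSMB would receive events whose serious label is unavailable to one arm.

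On G3, the one-arm estimate answers the descriptive aim in C2, and discontinuation of D-mannose has no control counterpart. Both points are right, and they are why the existing figures should stay. A between-arm comparison would also be imprecise (5 against 2 gives an interval that includes zero) and open to reporting bias without a placebo. That limits what the comparison can show, but it does not give the one-arm figure a background rate. G2 mentions an interim analysis of safety but gives no method for it, so it does not fill the gap.

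Two cautions remain. The 7.5% comes from a trial in women over 18, and B2 warns that earlier populations may differ from this one. Also, F3 3.e describes the weekly question as concerning symptoms related to study medication, whereas E3 3.e, F2 and F3 3.a describe it as covering any new symptoms. If the narrower form was sent, control reports may not be comparable. The forms are attachments outside these documents, so this cannot be settled here.

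**Conclusion.** Both parts hold. As written, a control's death or hospitalisation cannot be an SAE unless she takes D-mannose off protocol, and a serious event judged unrelated to D-mannose is not an SAE in any arm. The documents offer no basis for putting a number on how many events this would affect.

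The G3 side-effect figure meets its descriptive aim but cannot support attribution to D-mannose. At 5/60 it is compatible with an excess of 8.3 points or of none, depending on control counts that are assumed here. The point should be corrected, but it does not threaten the trial: no primary result or planned analysis changes.

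**What to change.** - **F3 3.d:** define an SAE by its outcome. Delete the study-drug condition from the SAE definition and the matching words in the hospitalisation sentence under Severe.
- **F3 3.d:** record relatedness separately on the existing scale, and state whether it refers to study drug or study procedures.
- **F3 3.e:** align the description of the weekly question with the any-new-symptoms form in E3 3.e, F2 and F3 3.a, so that both arms are asked the same thing.
- **G3:** keep the D-mannose-arm side-effect and discontinuation figures as descriptive. Add one table of AEs and SAEs by randomised arm, with the risk difference and 95% CI, labelled as open-label and subject to reporting bias.

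The cost is a few wording changes and one table, with no new data collection, visits or sample size, provided the any-new-symptoms question is the one in use. The drawbacks are a few more events classed as SAEs, some of them unrelated to D-mannose, and a comparison that may be imprecise and affected by open-label reporting.

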## ii      **Expectedness**

Less common: gastrointestinal upset symptoms (such as nausea, vomiting, flatulence, diarrhea, constipation, dyspepsia, and abdominal pain)

Rare: Rash or itching with medication.

## **3.e   Data Collection Procedures for Adverse Events**

Adverse events will be noted in each subject's file. Their text message response to the weekly question about new symptoms related to study medication will be reviewed in a timely fashion. If symptoms were noted by text message response, then a follow up phone call to the patient will be made.

## ***F4   Study Outcome Measurements and Ascertainment***

Outcomes will be measured by a weekly study diary with follow up as indicated and by the patient notifying the office if UTI like symptoms are experienced. Control checks to make sure a UTI was not missed are built into a six week follow up phone call and the three month follow up appointment.

## **G   Statistical Plan**

### ***G1   Sample Size Determination and Power***

We based our sample size estimate on assumptions for our primary aim, as this is the most important aim for providing information to support future recommendations and studies aimed at individualized patient care. The first published study on D-mannose was a RCT that showed 14.6% of rUTI patients develop another UTI while on treatment [9]. To be conservative in our sample size calculations, we assume 20% of patient on D-mannose will develop a UTI during the three-month treatment period. Very few studies have stated the percent of rUTI patients that develop another UTI while on vaginal estrogen therapy [27-29]. Due to the range of the published values, an average of these numbers was taken to arrive at an assumption that 45% of patients on only vaginal estrogen therapy will develop another UTI during the treatment period. We also accounted for a 10% dropout rate during the study period. Using these numbers to determine sample size, we calculated 60 patients would be needed per RCT arm for a total of 120 patients in the RCT. We recognize that our power for secondary aims is lower; however, we included these to begin to explore these other areas that are fundamental for understanding the underlying mechanism of D-mannose and how it works with rUTI. We have decided to also enroll 60 patients in the Observational arm of the study.

### ***G2   Interim Monitoring and Early Stopping***

In late 2019/early 2020 an interim analysis will be performed on the study data with all data to date serving as a "pilot" of the study. This will allow for interim analysis of safety and efficacy of the nutraceutical. The Haybittle-Peto rule will be followed for early stopping. Due to a slower recruitment rate than expected, an additional feasibility manuscript has been planned to inform the scientific community of these aspects of the trial. We would like to include a preliminary estimate of effect size and variability from interim analysis. The interim analysis rule is being used to avoid inflating type 1 error, but we expect to finish the trial as originally planned irrespective of the preliminary estimate, so no bias in study conduct should be introduced. The investigators will remain blinded to participants' assignment.

---

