## 2.h When and How to Withdraw Subjects

Withdrawal of subject as the result of subject decision:

- A subject enrolled in the study may decide to withdraw from the research at any time by notifying the principle investigator and/or another member of the research team by calling the office at [contact] and letting the office staff know she needs to speak to the principle investigator and/or member of the research team. The investigator speaking with the subject will clarify whether the subject wishes to withdraw from all components of the trial or only from a particular component of the trial. If the latter is desired, then follow-up data collection activities, for which the subject previously gave consent may continue.
- If a subject withdraws from the study then a member of the research team will ask the subject if she is willing to complete an study exit survey and/or the information that would have been gathered at the originally planned 3 month follow up appointment. This exit survey and 3 month follow up visit information may be obtained by appointment, by phone, or by mail.

Withdrawal of subject as the result of investigator decision:

- If an investigator terminates a subject's participation in the trial, the investigator should explain to the subject the reasons for this action and, as appropriate, other treatment options.
- If subjects were to have a serious adverse reaction to the medication, the investigator would recommend discontinuation of medication.

---

- An investigator may terminate a subject's participation in the study to protect a participant from excessive risk or risk with demonstrated lack of benefits or to maintain integrity of the data (for instance if a participant is not following study procedures or may be deliberately providing false information).
- If a subject is treated for an acute UTI during the 90 day study period without having an urine culture performed then data will be assessed both as if she did and did not have an acute UTI. She does not need to be withdrawn from the study as of the date of treatment of subjective UTI.. Antibiotics used for reasons other than UTI do not require subject withdrawal. Data obtained for any subject to the point of study withdrawal may be used in the study.

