### **3.d Preparation and Administration of Study Drug**

For the treatment arm of the RCT, the D-mannose powder will be ordered and distributed by the research team. The study team has selected NOW D-mannose pure powder as the D-mannose to be used in the RCT. The manufacturer label will be covered up/removed and a study label stating contents of a nutraceutical will be used to maintain patient blinding to which nutraceutical is being used.

For both arms of the RCT, the VET may be renewed or prescribed by a physician on the research team per routine clinical care. The patient will then pick up their prescription (vaginal cream, ring, or tablet) from their pharmacy of choice for continued use.

For the Observational arm of the study we will recommend the powdered D-mannose, but since participants will be purchasing their own D-mannose in the Observational arm they will be instructed to purchase either NOW D-mannose pure powder or NOW D-mannose 500 mg capsules. NOW will be the only brand patients are instructed to purchase, and example labels will be available for viewing by participants in the Observational arm to confirm they purchase the recommended D-mannose. We will communicate with the participants after they purchase their D-mannose of choice to record if powder or tablet and brand/manufacturer.

Medication (D-mannose, VET) will be self-administered by the patient. For patients using VET they will continue to use their VET as previously prescribed prior to enrollment in this study. On study day 1, if the patient is in an arm using D-mannose they will begin self administering D-mannose according to the instructions on the patient information handout. These instructions are as follows:

- **Powder specific instructions:** Dissolve one (1) teaspoon of the nutraceutical powder in at least 200 ml of water one time a day. (200 ml of water = 6.7 fluid ounces). Please attempt to take doses of the nutraceutical powder dissolved in water approximately 24 (twenty-four) hours apart. It is ok if you use a larger volume of water to dissolve the powder, but do not use any less than 200 ml of water. You MUST drink all of the water that the powder is dissolved in.”

---

- Capsule specific instructions: Take two 500 mg capsules (total of 1000 mg dose) every 12 hours.”

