All participants will be seen by a physician and research staff after 3 months in the study (when they have completed their 90 days in the study). At this visit, participants will be asked to bring their study diary and any unused D-mannose to their appointment (including empty bottles if more than one bottle was provided to a patient in order for a patient to have a 90 day supply of D-mannose). A 3 month follow up survey and exit survey will be given to the participant to fill out at the 3 month follow up appointment. Depending on participant convenience, this 3 month follow up survey can be completed at their appointment, by phone, or by mail. The survey will include questions on medication adherence. The study team will review the chart for any adverse events or UTIs not previously reported. Participants will fill out a questionnaire at this appointment to confirm the same. If a participant does not show for their 3 month follow up appointment then a member of the research team will attempt to contact the participant to reschedule this appointment. If a participant does not bring their study drug to their 3 month follow up, or if the participant is lost to follow up, then a reasonable attempt will be made to contact the patient and ask her to bring the study drug to the office. If a participant is lost to follow up then a reasonable attempt will be made to see if the participant is willing to complete a 3 month follow up survey and/or exit survey over the phone or by mail. If the participant does not complete all 90 days of the study, or if they forget to bring their study diary to their 3 month follow up appointment, then she will be offered the alternative of mailing or faxing her study diary to the office. If a participant completed the study early then she will be asked if she is willing to complete the 3 month follow up appointment information and exit survey at their next office visit, by phone, or by mail.

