### 3.h Receiving, Storage, Dispensing and Return

After receiving the purchased D-mannose, it will be stored in a secure area for each of the four outpatient locations for the Washington University Physicians Women's Center for Bladder and Pelvic Health and in a secure area in the academic offices for the Washington University Division of Female Pelvic Medicine and Reconstructive Surgery. D-mannose should be stored in a cool place where the container is kept dry and tightly closed. It should be stored away from extreme heat.

The only medication that will be dispensed to study participants during the course of this study will be D-mannose to patients in the treatment arm of the RCT. Once a subject is randomized to the treatment arm, they will receive D-mannose in its original packaging but

---

relabelled as Nutraceutical to maintain patient blinding to which nutraceutical is being tested in the smallest quantity available to meet the amount required for a 90 day supply. For example, many manufacturers only distribute powder D-mannose in 42 day or 80 day supply bottles. In this situation, one 80 day and one 42 day bottle of D-mannose will be given to the patient in order to meet the 90 day required supply for the study. The medication that is not used will be brought to the patient's 3 month follow up appointment to be weighed.

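### The interim-analysis section says investigators stay blinded to assignment, but the design gives them no blind, and nobody is named to run or see the efficacy look

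*Combined protocol and SAP*

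**What the plan says.** Section G2 schedules an interim analysis by calendar date, covering safety and efficacy, under the Haybittle-Peto rule. It adds a feasibility manuscript, in which the authors would like to give a preliminary effect size. It argues that conduct will not be biased because they expect to complete the trial whatever the estimate shows. It closes with "The investigators will remain blinded to participants' assignment".

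Elsewhere the protocol describes a different situation:

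- E3 3.g: "The research team will not be blinded to the study drug. There are no placebos being used in this study".
- E3 3.d: for the treatment arm, "the D-mannose powder will be ordered and distributed by the research team".
- E3 3.h: the only medication handed out "will be D-mannose to patients in the treatment arm of the RCT".
- E2 2.e: after consent, an envelope naming the group is opened.
- E2 2.h: a woman withdraws by "notifying the principle investigator and/or another member of the research team", which counts the principal investigator as part of the team.
- E3 3.e: at the 3-month visit, with a physician and research staff, "participants will be asked to bring their study diary and any unused D-mannose to their appointment".

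The only masking described outside G2 is of participants, and only to which nutraceutical is being studied (E3 3.d, 3.f, 3.g, 3.h and G5).

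**The concern.** A reader of G2 would conclude that the people running the trial do not know who is on D-mannose. On the rest of the protocol, they do. That matters most at an interim efficacy look, because staff could then know both each woman's arm and the direction of the effect so far.

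The primary outcome is open to this. It begins with a symptom report (F4). The team follows up each positive symptom text and makes a six-week call that covers study medication and outside UTI treatment together (E3 3.e). At the end, "The study team will review the chart for any adverse events or UTIs not previously reported". Specimens are taken only when clinically indicated (F2), so whether a culture exists depends partly on the same clinic. G2's argument about finishing regardless addresses selective stopping. It does not address uneven ascertainment after the look.

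**Working it through.** **1. Can both blinding statements be true?** Two softer readings were tried.

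- E3 3.g might mean only that staff know which product is used. The same staff still give an unmasked product to one arm with no comparator, so they know the arm.
- G2 might mean only that the interim dataset is coded. It does not say so, and no section describes a shielded analyst or investigator.

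Neither reading removes the conflict.

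**2. Who runs and sees the look?** G2 names nobody. F3 3.b ii makes data available to a DSMB for independent analysis, and the DSMB includes a biostatistician. That sequence starts from a review of adverse events and is triggered by participant counts (first ten, half, all), not by G2's date. It mentions neither efficacy nor the stopping rule. F3 3.a and H1 otherwise limit data access to the research team.

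**3. The plan's own sample size.** G1 gives risks of 20% and 45%, 10% dropout and 60 per arm. Two-sided 5% alpha and 80% power are assumed here, because G1 states neither. With mean risk 0.325:

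n = [1.96·√(2·0.325·0.675) + 0.842·√(0.45·0.55 + 0.20·0.80)]² / 0.25² = 53.9, so 54 per arm; 54/0.90 = 60. G1's figure reproduces.

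**4. Is numerical alpha inflation the problem?** No. Assume an interim boundary of p < 0.001 and a final test at 0.05. Overall alpha is then 0.0506 to 0.0500 for information fractions 0.25 to 0.75.

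**5. Precision of the interim estimate.** The interim size is not stated, so n = 20, 30 and 40 per arm are assumed, at the G1 risks.

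- Risk difference: 1.96·√[(0.20·0.80 + 0.45·0.55)/n]
- Pooled event rate: 1.96·√[(0.20·0.80 + 0.45·0.55)/(4n)]

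| n per arm | Half-width, risk difference | Half-width, pooled rate |
|---|---|---|
| 20 | 28.0 points | 14.0 points |
| 30 | 22.8 points | 11.4 points |
| 40 | 19.8 points | 9.9 points |

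**6. Illustration of what uneven detection could do.** Assume no true effect, 45% risk in both arms, 54 analysed per arm, and a two-sided 5% chi-squared test without continuity correction, evaluated by exact enumeration. Detection falls by a relative amount d, only in the 54 − n later D-mannose women. Bias in the risk difference = 0.45·d·(54 − n)/54.

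| n | Bias, d = 10% | Bias, d = 20% | Rejection, d = 10% | Rejection, d = 20% |
|---|---|---|---|---|
| 20 | 2.8 points | 5.7 points | 5.5% | 8.6% |
| 30 | 2.0 points | 4.0 points | 5.0% | 6.5% |
| 40 | 1.2 points | 2.3 points | 4.7% | 5.2% |

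Without any loss the rejection rate is 4.5%. At 20% risk in both arms it goes from 5.1% to at most 6.3%. With all 60 per arm analysed at 45% risk it goes from 5.4% to between 5.6% and 10.5%.

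**The case against.** **Section 3.g is not the strongest evidence.** It speaks of the drug, while G2 speaks of assignment. That is fair, but the envelope in E2 2.e and the one-arm distribution in E3 3.d and 3.h settle the matter.

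**The protocol has real safeguards.** Infections must be culture-proven (C1). Texts go out on fixed days with automatic entry, all arms have the same contacts, and participants complete their own questionnaire (E3 3.e). For an infection treated without culture, "data will be assessed both as if she did and did not have an acute UTI" (E2 2.h). A positive text that is poorly followed up therefore leaves a trace. This limits the risk, but the safeguards do not recover an episode that is neither reported nor treated, which prompting at the six-week call or final visit might have brought out.

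**The detection-loss scenario is arbitrary.** Its size, its direction and the interim n are all assumed, and it lowers detection even when the interim does not favour D-mannose. If loss occurs only after a favourable interim (44% to 46% of the time under that null), the average bias drops to about 0.5 to 2.5 points, while rejection becomes 5.2% to 9.6%. It shows only what such a loss could do.

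**Staff have known the arm since day 1.** This is true, and the documents cannot separate that risk from anything the interim adds.

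**A stopping rule and an expectation to finish can coexist.** They are not flatly contradictory, but completing irrespective of the estimate leaves the rule's role unclear.

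**Conclusion.** The concern holds, with high confidence on the text. G2 asserts a blind that the design does not provide, and the plan does not say who conducts or sees the interim efficacy analysis. It should be fixed before that analysis.

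The size of any added bias is unknown. Under the assumptions above, the rejection rate ranges from near nominal (4.7%) to 8.6% at 54 per arm and 45% risk, and all of that loss is attributed to interim knowledge. The benefit of releasing the by-arm estimate early is small: its half-width of about 20 to 28 points is comparable with the 25-point difference the trial is designed to detect.

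**What to change.** In G2, replace the blinding sentence with: *The RCT is open-label to the research team; participants are masked only to the identity of the nutraceutical.*

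Then add: *The by-arm interim efficacy analysis is run by the DSMB biostatistician and seen only by the DSMB until the last participant's day 90. The research team does not tabulate outcomes by arm before then.*

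Until that date, the feasibility manuscript should report recruitment, retention, adherence and the pooled event rate with the RCT arms combined. G2 should also reconcile the Haybittle-Peto rule with the expectation of finishing irrespective of the estimate. F3 3.b ii should say whether the DSMB's remit covers efficacy, and the access wording in F3 3.a and H1 should allow the export.

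The cost is these wording changes and one data export to a biostatistician already on the DSMB. The by-arm estimate, which would serve the C2 aim of informing future studies, waits for the final report. The ban on tabulating by arm relies on discipline, since the team holds the data and knows the arms. The open-label risk present from day 1 remains.
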